#### **5.7.2 Number of discontinuations due to AEs**

The percent of patients who have been withdrawn for the study due to AEs will be compared between the two treatment groups using Fisher's exact test.

#### **5.7.3 Hematology and biochemistry**

Hematology and biochemistry data will be summarized by using descriptive statistics at each assessment by treatment group. Change from baseline to each follow-up assessment will also be summarized by using descriptive statistics by treatment group. The data listings of patients who have abnormal values as well as patients who have clinically significant values will be produced for each parameter. The number (%) of patients who have ALT > 2 x ULN, 3 x ULN, and 5 x ULN during the study will be compared between the two treatment groups.

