#### 4.3 Exclusion Criteria

Individuals will be excluded from enrollment if they meet **any** of the following criteria:

1. Prior use of iron chelation
2. Diagnosis of hepatitis B or C, or HIV infection
3. Evidence of abnormal liver or kidney function at screening (serum ALT level > 5 times upper limit of normal or creatinine levels >2 times upper limit of normal)
4. Disorders associated with neutropenia (ANC < 1.5 x 10^9/L) prior to the initiation of study medication

*Exception:* Patients whose neutropenia is attributed by the treating physician to episodes of infection or to drugs associated with a decline in the neutrophil count and in whom the ANC has returned to a normal level at the screening visit.

6. A serious, unstable illness, as judged by the investigator, during the past 3 months before screening/baseline visit including but not limited to hepatic, renal, gastro-enterologic, respiratory, cardiovascular, endocrinologic, neurologic or immunologic disease.
7. History of allergy or sensitivity to any components of the study product or related compounds.
8. Receipt of any investigational products within the past 30 days or 5 half-lives (whichever is longer) preceding the first dose of study medication.
9. Participation in any investigational clinical study, other than observational, within the past 30 days; or plans to participate in such a study at any time from the day of enrollment until 30 days post-treatment in the current study.
10. Presence of any medical condition which in the opinion of the investigator would cause participation in the study to be unwise.
11. Identified as a child, either biological or legally adopted, of an investigator or other site staff directly affiliated with this study.

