**V: Verify**

-  Visits are scheduled every 30 days ( $\pm$  10 days).
-  Patients terminate from the study at Month 12 or when they have been found to have a serum ferritin level  $\geq$  1000  $\mu$ g/L at 2 consecutive visits, whichever comes first.
-  Hematology: Hemoglobin, total WBC count, ANC, MCV, and platelet count.
-  Blood chemistry: Total protein, GGT, glucose, bilirubin (total, direct, and indirect), AST, ALT, albumin, blood urea nitrogen, calcium, creatinine, total iron binding capacity, serum iron, zinc, and CRP.
-  The results obtained at screening for blood chemistry, physical examination, and urinalysis are considered to be the baseline results. These tests are not repeated at Day 0.
-  A blood sample for DNA testing is to be taken only if DNA confirmation of a diagnosis of beta-thalassemia is not available at the time of screening.
-  Urinalysis: pH, specific gravity, glucose, protein, ketones, blood, and (if indicated by the dipstick results), sediment microscopy. If there is blood in the urine or three or more “plus signs” for protein, samples must be sent for microscopy.
-  Hepatitis B, hepatitis C, and HIV.
-  Heart rate, blood pressure, and body temperature. At the time of these measurements, the child must be calm and not crying.
-  For infants not yet able to stand upright, stature is measured as recumbent length.
-  For TSAT and SF, the values obtained at the screening visit (not those obtained at baseline) are used for the eligibility criteria.
-  Blood samples for the assessment of prolactin are taken pre-dose and at  $+ 1.5$  h  $\pm$  5 minutes post-dose. The second set of samples are taken only from patients who are still in the study at Month 12; they are not taken from patients who are terminated before that time.
-  Dosing: Deferiprone oral solution 80 mg/mL or matching placebo solution.

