### 4.2.2 Laboratory Measurements

Analyses are performed at a central laboratory, with the exception of the weekly or biweekly hematology assessments which may be performed at a local laboratory. Investigators interpret each report promptly (preferably within 24 hours) and document their review by signing or initialing and dating it. Any laboratory values that fall outside a clinically accepted range, or that differ significantly from previous values, are assessed for clinical significance, and are marked by the investigator as either “CS” (clinically significant) or “NCS” (not clinically significant). Any clinically significant abnormalities or changes that are not part of a larger medical condition that is already recorded are further explained on the laboratory report and documented as an adverse event in the eCRF.

Samples for laboratory safety assessments are taken at the time points indicated below. If a patient withdraws from the study, the End of Study procedures are to be performed at an early termination visit.

Hematology: Hemoglobin, total WBC count, ANC, MCV, and platelet count	Screening and weekly after start of dosing up to Month 6 visit, then biweekly until Month 12 or early termination from the study
Blood chemistry: Total protein, GGT, fasting glucose, bilirubin (total, direct, and indirect), AST, ALT, albumin, blood urea nitrogen, calcium, creatinine, total iron binding capacity, serum iron, zinc, and C-reactive protein (CRP)	Screening and Months 1, 3, 6, 9, and 12 (or end of study)

Urinalysis: pH, specific gravity, glucose, protein, ketones, blood, and (if indicated by the dipstick results), sediment microscopy. If there is blood in the urine or three or more “plus signs” for protein, samples must be sent for microscopy.	Screening and Month 12 (or end of study)
Serology: Hepatitis B, hepatitis C, HIV	Screening
Other: Prolactin	Baseline and Month 12

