#### **14.3.6.2 Biochemistry**

Table 14.3.6.2.1 Biochemistry data at each assessment

Table 14.3.6.2.2 Change in biochemistry data from baseline to at each follow-up assessment

Table 14.3.6.2.3 Shift table for biochemistry data: deferiprone group

Table 14.3.6.2.4 Shift table for biochemistry data: placebo group

Table 14.3.6.2.5 Percent of patients who had ALT > 2 x ULN, 3 x ULN, or 5 x ULN during the study

Table 14.3.6.2.6 Percent of patients who had AST > 2 x ULN, 3 x ULN, or 5 x ULN during the study

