### 14.3.6.2 Biochemistry

Table 14.3.6.2.1 Albumin at each assessment

	Deferiprone		Placebo		P-value (t-test)
	N	Mean $\pm$ SD (Min, Max)	N	Mean $\pm$ SD (Min, Max)	
Baseline	xx	xx.x $\pm$ xx.x (xx.x,xx.x)	xx	xx.x $\pm$ xx.x (xx.x,xx.x)	0xxxx
Month 1	xx	xx.x $\pm$ xx.x (xx.x,xx.x)	xx	xx.x $\pm$ xx.x (xx.x,xx.x)	0xxxx
Month 3	xx	xx.x $\pm$ xx.x (xx.x,xx.x)	xx	xx.x $\pm$ xx.x (xx.x,xx.x)	0xxxx
Month 6	xx	xx.x $\pm$ xx.x (xx.x,xx.x)	xx	xx.x $\pm$ xx.x (xx.x,xx.x)	0xxxx
Month 9	xx	xx.x $\pm$ xx.x (xx.x,xx.x)	xx	xx.x $\pm$ xx.x (xx.x,xx.x)	0xxxx
Month 12	xx	xx.x $\pm$ xx.x (xx.x,xx.x)	xx	xx.x $\pm$ xx.x (xx.x,xx.x)	0xxxx

Data source: 16.2.8.4 Listing of biochemistry

Note: Similar tables will be produced for total protein, GGT, glucose, bilirubin (total, direct, and indirect), AST, ALT, blood urea nitrogen, calcium, creatinine, total iron binding capacity, serum iron, and zinc.

Table 14.3.6.2.2 Change in albumin from baseline to at each follow-up assessment

	Deferiprone		Placebo		
	N	Mean ± SD (Min, Max)	N	Mean ± SD (Min, Max)	P-value (T-test)
Month 1	xx	xx.x ± xx.x (xx.x,xx.x)	xx	xx.x ± xx.x (xx.x,xx.x)	0.xxxx
Month 3	xx	xx.x ± xx.x (xx.x,xx.x)	xx	xx.x ± xx.x (xx.x,xx.x)	0.xxxx
Month 6	xx	xx.x ± xx.x (xx.x,xx.x)	xx	xx.x ± xx.x (xx.x,xx.x)	0.xxxx
Month 9	xx	xx.x ± xx.x (xx.x,xx.x)	xx	xx.x ± xx.x (xx.x,xx.x)	0.xxxx
Month 12	xx	xx.x ± xx.x (xx.x,xx.x)	xx	xx.x ± xx.x (xx.x,xx.x)	0.xxxx

Data source: 16.2.8.4 Listing of biochemistry

Note: Similar tables will be produced for total protein, GGT, glucose, bilirubin (total, direct, and indirect), AST, ALT, blood urea nitrogen, calcium, creatinine, total iron binding capacity, serum iron, and zinc.

Table 14.3.6.2.3 Shift table for albumin at baseline vs last assessment: deferiprone group

		Baseline			P-value (McNemar-Bowker's test)
	N (%)	Low	Normal	High	
Last assessment	Low	xx (xx)	xx (xx)	xx (xx)	0.xxxx
	Normal	xx (xx)	xx (xx)	xx (xx)	
	High	xx (xx)	xx (xx)	xx (xx)	

Data source: 16.2.8.4 Listing of biochemistry

Note: Similar tables will be produced for total protein, GGT, glucose, bilirubin (total, direct, and indirect), AST, ALT, blood urea nitrogen, calcium, creatinine, total iron binding capacity, serum iron, and zinc.

Table 14.3.6.2.4 Shift table for albumin at baseline vs last assessment: placebo group

		Baseline			P-value (McNemar-Bowker's test)
	N (%)	Low	Normal	High	
Last assessment	Low	xx (xx)	xx (xx)	xx (xx)	0.xxxx
	Normal	xx (xx)	xx (xx)	xx (xx)	
	High	xx (xx)	xx (xx)	xx (xx)	

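### The ALT > 2x and > 3x ULN counts, and all three AST counts, carry no baseline condition, so any child already above a limit at entry is counted as a case and weakens the hepatic comparison

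*SAP*

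**What the plan says.** The text of SAP 5.7.3 plans a between-arm comparison of "The number (%) of patients who have ALT > 2 x ULN, 3 x ULN, and 5 x ULN during the study". It names ALT only. AST enters through the table list in SAP 14.3.6.2: "Percent of patients who had AST > 2 x ULN, 3 x ULN, or 5 x ULN during the study". The shells for both tables (headed 14.2.6.2.5 and 14.2.6.2.6 there, 14.3.6.2.5 and 14.3.6.2.6 in the list) assign Fisher's exact test. Neither the text nor the shells refer to post-baseline or treatment-emergent values.

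Protocol 4.3 excludes a child with "serum ALT level > 5 times upper limit of normal" at screening. It states no AST limit.

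SAP Table 1, footnote 5, fixes the baseline: "The results obtained at screening for blood chemistry, physical examination, and urinalysis are considered to be the baseline results". Chemistry is not repeated on Day 0; follow-up samples are due at Months 1, 3, 6, 9 and 12 or end of study (SAP 4.2.2).

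Some baseline-referenced output is planned. SAP 5.7.3 adds "Change from baseline to each follow-up assessment will also be summarized by using descriptive statistics by treatment group". The shells give Low/Normal/High shift tables of baseline against last assessment within each arm, and their note says "Similar tables will be produced for total protein, GGT, glucose, bilirubin (total, direct, and indirect), AST, ALT" and other analytes.

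**The concern.** The ULN-multiple tables are the only planned output that grades liver enzymes by size of elevation and compares the arms. A child with ALT at 4x ULN at screening who stays there is a case in the > 2x and > 3x rows of whichever arm was assigned, and says nothing about the drug.

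The SAP also leaves open whether the screening value falls within the study period. If it does, every child elevated at entry is a case automatically. If it does not, the child is a case only if a later value is also above the limit. Two programmers could produce different tables from the same data.

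The comparison matters because safety is the trial's secondary objective and raised ALT is among the more frequent reactions in Protocol Table 1.1. A rise caused by treatment would be harder to see against a background present before dosing.

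**Working it through.** **Which rows are exposed.** Compare each reporting limit with the entry rule:

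| Row | Can an eligible child be above it at screening? |
|---|---|
| ALT > 2x, ALT > 3x | Yes; only ALT > 5x excludes |
| ALT > 5x | No |
| AST > 2x, > 3x, > 5x | Yes; no AST entry limit is stated |

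**Inputs from the documents.** 32 children per arm (SAP 3.2); Fisher's exact test (shells); two-sided 0.05 (SAP 5). The only ALT rate on deferiprone is 65/860 = 7.6% (Protocol Table 1.1), which is an adverse-reaction term and not a ULN multiple. The plan gives no power or expected rate for this comparison, so there is no figure to reproduce first.

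**Assumptions.** The documents do not give the share of children above a limit at entry, so I take 0 to 3 children per arm in the worked counts and b = 0% to 20% in the power figures. New-elevation rates are also assumed. Every child elevated at entry is taken to remain a case, which is the upper end of the dilution.

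**Worked counts.** Suppose treatment adds 6 new cases against 0:

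| Elevated at entry, per arm | As planned | p | New cases only | p |
|---|---|---|---|---|
| 0 | 6/32 v 0/32 | 0.024 | 6/32 v 0/32 | 0.024 |
| 1 | 7/32 v 1/32 | 0.053 | 6/31 v 0/31 | 0.024 |
| 3 | 9/32 v 3/32 | 0.107 | 6/29 v 0/29 | 0.023 |

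**Power.** With e the new-elevation rate, the planned count has rate b + (1 − b)e in each arm. For b = 10% and e = 30% v 2%:

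- deferiprone: 0.10 + 0.90 × 0.30 = 37.0%
- placebo: 0.10 + 0.90 × 0.02 = 11.8%
- risk ratio: 37.0/11.8 = 3.1, against 30/2 = 15 for new cases alone

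Exact Fisher power, planned count on 32 per arm against new cases among children not elevated at entry (30, 29 and 26 per arm at b = 5%, 10% and 20%):

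| New rates | b | Risk ratio as planned | Power as planned | Power, new cases only |
|---|---|---|---|---|
| 30% v 2% | 5% | 4.9 | 70% | 81% |
| 30% v 2% | 10% | 3.1 | 57% | 78% |
| 30% v 2% | 20% | 2.0 | 39% | 75% |
| 20% v 2% | 10% | 2.4 | 27% | 38% |
| 20% v 2% | 20% | 1.7 | 18% | 33% |
| 7.6% v 2% | 5% to 20% | 1.8 to 1.2 | 3% to 4% | about 1% |

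At b = 0 the two counts coincide.

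**At the documents' own rate.** 7.6% of 32 is 0.076 × 32 = 2.4 cases. With the restricted count, 2/29 v 0/29 gives p = 0.49 and 3/29 v 0/29 gives p = 0.24. Neither count would show a difference.

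**The case against.** The strongest reply is that the SAP already looks at liver enzymes relative to baseline. It plans change from baseline, shift tables for ALT and AST, and listings of abnormal values. The shells give the baseline maximum by arm, which would show whether any child entered well above normal. Adverse events are compared by Fisher's exact test for each preferred term; they are collected only after dosing starts, and a pre-existing condition that does not worsen is not one. The child who stays at 4x ULN shows no change, no shift and no event in those outputs.

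That stands in part. These outputs limit the harm, but none gives a between-arm count of new threshold crossings:

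- Mean changes do not identify individual crossings.
- The shift tables use one High category and only the last assessment. A rise from above 2x to above 5x is High at both times, and a mid-study peak that resolves is missed.
- Listings do not compare the arms.
- The adverse-event route depends on the investigator's judgement of clinical significance.

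Two further objections stand in full. Entry prevalence is unknown and may be nil, since hepatitis B and C, HIV and prior chelation are excluded. And 6 new cases in 32 is 18.8%, well above the 7.6% in Table 1.1.

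A reader might infer that all the ALT and AST counts do contain pre-existing elevations because of the ALT entry rule, and so hide a real hepatic signal. The documents do not support that. The ALT > 5x row cannot be diluted this way. The ALT rule says nothing about AST, which is exposed only because no AST limit is stated. No document reports that any child entered above a limit, or that a signal exists.

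**Conclusion.** The point holds as a conditional gap in safety reporting. ALT > 2x and > 3x, and AST at all three limits, are counted without reference to baseline although eligibility permits children to start above them. ALT > 5x is not affected.

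If some children are elevated at entry, randomisation makes that background equal in expectation, so it attenuates the contrast and adds noise without biasing the comparison when there is no effect. The size runs from nothing (none elevated) to a fall in power from 78% to 57% (10% elevated, new rates 30% v 2%). In the 6 v 0 example, one pre-existing case per arm moves p from 0.024 to 0.053. These sizes rest on assumed entry prevalence, assumed new-case rates, and every child elevated at entry remaining a case. At new-case rates near 7.6% the sample is too small under either count. No efficacy analysis is touched. It is worth making as a minor improvement, not a flaw that threatens the trial's conclusions.

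**What to change.** In SAP 5.7.3 and in both ULN-multiple tables:

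1. For ALT and AST, count children with a post-baseline value above each multiple among those at or below that multiple at screening, the defined baseline. This also settles whether the screening value counts.
2. Add a row giving, by arm, the number already above each multiple at screening.
3. Add a by-arm shift table of screening against worst post-baseline value in the bands ≤ 2x, > 2–3x, > 3–5x and > 5x ULN. Without it, the restricted count would hide worsening in children already above a limit. A rise from 3.1x to 4.9x ULN, for example, would appear in no row of the restricted count, and movement inside one band still would not show in the shift table.

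The cost is a sentence or two in the SAP, one shell row and one extra table, all from data already collected. The denominators become slightly smaller and can differ from row to row. No gain in power should be expected if new elevations occur at about the Table 1.1 rate.

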#### **5.7.4 Urinalysis**

Urinalysis assessments consist of pH, specific gravity, glucose, protein, ketones, blood, and (if indicated by the dipstick results), sediment microscopy. If there is blood in the urine or three or more "plus signs" for protein, samples must be sent for microscopy. Clinically significant laboratory values for urinalysis are reported as AEs.

#### **5.7.5 Vital signs**

Temperature, resting heart rate, and diastolic and systolic blood pressures will be summarized using descriptive statistics at each assessment by treatment group. Change from baseline to each follow-up assessment will be also summarized using descriptive statistics by treatment group.

### **5.7.6 Prior and concomitant medications**

Prior and concomitant medications are summarized using the WHO Drug Dictionary (WHO-DD) version B2 (March 2018).

### **5.7.7 Time to withdrawal**

A Kaplan-Meier survival curve for the time to be withdrawn from the study will be generated for the two treatment groups. The Log-rank test will be used for comparing the two survival curves.

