#### 4.5 Patient Withdrawal

Patients/parents have the right to withdraw/withdraw their child from the study at any time and for any reason without consequence to future care by the investigator or study center.

A patient may be withdrawn from the study at any time, at the discretion of the investigator, for any of the following reasons:

- Medical or safety reasons considered significant by the parent/legal guardian (or patient, if applicable) and/or the investigator
- Requirement for concomitant medication that might interfere with the evaluation of study treatment or may be contraindicated
- Occurrence of other illnesses that might affect the patient's further participation in the study or evaluation of study treatment
- A protocol deviation that might interfere with study assessments, as judged by the investigator
- Repetitive non-compliance with the protocol or with instructions of the investigator
- Participation in another clinical trial at any time during the conduct of this study
- Any other situation where, in the opinion of the investigator, continuation of the study would not be in the best interest of the patient

A patient **must** be withdrawn from the study if any of the following conditions apply:

- Attainment of a serum ferritin level  $\geq 1000 \mu\text{g/L}$  at 2 consecutive visits (provided that the child has had no signs of infection in the previous 7 days and that CRP level is not greater than 20% higher than the normal range for the patient's age)
- Occurrence of moderate neutropenia or of severe neutropenia/agranulocytosis (see [Section 7.2.1.8.1](#))
- Occurrence of any adverse event characterized as life-threatening or disabling that is not associated with the patient's condition

- Receipt of a rescue medication (see [Section 4.7](#))
- Termination of the study by the sponsor

Parents/legal guardians who decide to withdraw their child from the study (or, in the case of a child who is able to communicate this, a patient who wishes to withdraw) should always be contacted, if possible, in order to ask about the reason for withdrawal, whether any adverse events (AEs) occurred, and use of concomitant medications. A withdrawn patient should return for an Early Termination visit. All investigational product and materials should be returned. If any AEs occurred, the investigator must attempt to follow up on the outcome until resolution or for 30 days post-termination, whichever comes first.

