#### 4.1.1 Serum Ferritin ( $\mu\text{g/L}$ )

Ferritin is a protein that stores iron in a non-toxic form, transports it to areas where it is required, and releases it in a controlled manner, thereby acting as a buffer against iron deficiency and iron overload. It is mainly found in tissues, but small amounts are measured in the serum, where it can serve as an indirect but easily measurable marker of the total amount of iron stored in the body. (Drawbacks of using it as a marker include lack of specificity, as disorders other than iron overload can cause large amounts of ferritin to be released into the circulation, and inter-patient variability.) Levels of serum ferritin above 1000 ng/mL are often considered to be associated with iron toxicity. In young children who have only recently begun an RBC transfusion regimen, it takes some time for this level to be reached, but in the absence of chelation it inevitably is reached.

Serum ferritin is measured at each visit, and the time to reach a level  $\geq 1000 \mu\text{g/L}$  will be compared between the treatment arms. Patient is to be withdrawn from the study when they attain a serum ferritin level  $\geq 1000 \mu\text{g/L}$  at 2 consecutive visits provided that the child has had no signs of infection in the previous 7 days and that CRP level is not greater than 20% higher than the normal range for the patient's age.

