## **5. Statistical Analysis**

A two-sided p-value of 0.05 will be used as the significance level for the determination of statistical significance in all statistical tests.

All statistical analyses of efficacy and safety data will be performed using SAS (version 9.4 or higher) on the Windows operating system.

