### **5.2.2 Secondary Efficacy Endpoints**

The secondary efficacy endpoints are:

- The percentage of patients whose serum ferritin level is still less than 1000  $\mu\text{g}/\text{L}$  at each visit
- The percentage of patients whose LPI value is still less than 0.6  $\mu\text{M}$  at each visit
- The percentage of patients whose TSAT value is still less than 60% at each visit
- Time to reach a serum ferritin level  $\geq 1000 \mu\text{g}/\text{L}$  (Note: a patient is to be withdrawn from the study only if the repeated serum ferritin level is  $\geq 1000 \mu\text{g}/\text{L}$ .)
- Time to reach an LPI value  $\geq 0.6 \mu\text{M}$
- Time to reach a TSAT value  $\geq 60\%$

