## 14.1 Patient disposition, demographics, and baseline data

Table 14.1.1 Patient disposition

	Deferiprone	Placebo	P-value (Fisher's exact test)
Randomized	xxx	xxx	
Exposed	xxx (xx%)	xxx (xx%)	0.xxxx
Completed	xxx (xx%)	xxx (xx%)	0.xxxx
Withdrawn	xxx (xx%)	xxx (xx%)	0.xxxx

Data source: 16.2.1.1 Listing of disposition

Table 14.1.2 Number of patients by study site

Country	Site	Deferiprone	Placebo	Total
Egypt	003	xx	xx	xx
	004	xx	xx	xx
	005	xx	xx	xx
Indonesia	006	xx	xx	xx
	Total	xx	xx	xx

Data source: 16.2.4.1 Listing of demographics

Table 14.1.3 Number of patients in safety, ITT, and PP populations

		Deferiprone	Placebo
Safety population		xx	xx
ITT population	Serum ferritin	xx	xx
	LPI	xx	xx
	TSAT	xx	xx
PP population	Serum ferritin	xx	xx
	LPI	xx	xx
	TSAT	xx	xx

Data source: 16.2.3.1 Listing of assignment of patients to analysis sets

Table 14.1.4 Reasons for not completing the study

		Deferiprone	Placebo	Total
		n (%)	n (%)	n (%)
N		xx (100)	xx (100)	xx (100)
Reason:	Detail			
Adverse event	Ccccc	xx (xx)	xx (xx)	xx (xx)
	Ccccc	xx (xx)	xx (xx)	xx (xx)
Withdrawal by parent/guardian	Ccccc	xx (xx)	xx (xx)	xx (xx)
	Ccccc	xx (xx)	xx (xx)	xx (xx)
Lost to follow-up	Ccccc	xx (xx)	xx (xx)	xx (xx)
	Ccccc	xx (xx)	xx (xx)	xx (xx)
Physician decision	Ccccc	xx (xx)	xx (xx)	xx (xx)
	Ccccc	xx (xx)	xx (xx)	xx (xx)
Protocol deviation	Ccccc	xx (xx)	xx (xx)	xx (xx)
	Ccccc	xx (xx)	xx (xx)	xx (xx)
Lack of efficacy	Ccccc	xx (xx)	xx (xx)	xx (xx)
	Ccccc	xx (xx)	xx (xx)	xx (xx)
Other	Ccccc	xx (xx)	xx (xx)	xx (xx)
	Ccccc	xx (xx)	xx (xx)	xx (xx)
Total		xx (xx)	xx (xx)	xx (xx)

Data source: 16.2.1.1 Listing of disposition

Table 14.1.5 Demographics data

	Deferiprone	Placebo	Total	
N	xx	xx	xx	p-value §
Age (years):				0xxxx
Mean	xx.x	xx.x	xx.x	
SD	xx.x	xx.x	xx.x	
Minimum	xx.x	xx.x	xx.x	
Maximum	xx.x	xx.x	xx.x	
Sex: n (%)				0xxxx
Female	xx (xx)	xx (xx)	xx (xx)	
Male	xx (xx)	xx (xx)	xx (xx)	
Ethnic Origin: n (%)				0xxxx
Hispanic/Latino	xx (xx)	xx (xx)	xx (xx)	
Not Hispanic/Latino	xx (xx)	xx (xx)	xx (xx)	
Racial Origin: n (%)				0xxxx
Asian	xx (xx)	xx (xx)	xx (xx)	
American Indian or Alaska Native	xx (xx)	xx (xx)	xx (xx)	
Black or African American	xx (xx)	xx (xx)	xx (xx)	
Native Hawaiian or Other Pacific Islander	xx (xx)	xx (xx)	xx (xx)	
White	xx (xx)	xx (xx)	xx (xx)	
Other	xx(xx)	xx(xx)	xx(xx)	

§T-test for age; Fisher's exact test for sex, ethnic origin, and racial origin

Data source: 16.2.4.1 Listing of demographics

Table 14.1.6 Medical history

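### The all-cause time-to-withdrawal log-rank in SAP 5.7.7 sits under safety but is dominated by mandatory exits for serum ferritin of 1000 µg/L or more, so it mostly repeats the efficacy comparison and cannot be interpreted for tolerability

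*SAP*

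**What the plan says.** SAP 5.7.7 consists of two sentences: "A Kaplan-Meier survival curve for the time to be withdrawn from the study will be generated for the two treatment groups", and "The Log-rank test will be used for comparing the two survival curves". It does not define the event, restrict the reason or state a censoring rule. SAP Section 5 applies to it as to every test: "A two-sided p-value of 0.05 will be used as the significance level".

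Reaching the SF threshold is itself a withdrawal. Under Protocol 4.5 a patient must "be withdrawn from the study if any of the following conditions apply", and the first condition listed is "Attainment of a serum ferritin level" of at least 1000 µg/L at two consecutive visits, subject to infection and CRP checks. SAP 4.1.1 uses the same verb: "Patient is to be withdrawn from the study when they attain a serum ferritin level" of that size. So does the note in SAP 5.2.2: "a patient is to be withdrawn from the study only if the repeated serum ferritin level is" at or above the threshold.

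Related analyses are planned elsewhere:
- SAP 5.6 has a log-rank on time to SF of 1000 µg/L or more, as an efficacy analysis.
- SAP 5.7.2 compares the percentage withdrawn because of AEs by Fisher's exact test, and Table 14.3.1.1 has a row with a p-value for it.
- SAP 5.7.1 lists AE withdrawals with their timing.
- Table 14.1.4 tabulates reasons for not completing by arm. It includes "Lack of efficacy" and a detail column, but no row for the SF threshold.

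Time to withdrawal is not among the safety endpoints in SAP 5.3 and has no counterpart in Protocol 9.4.1.4. In the SAP's list of outputs it appears only as SAS output 16.1.9.4.

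**The concern.** The event in 5.7.7 mixes two kinds of exit that are expected to run in opposite directions. Exits for SF are treatment failures and should be far more common on placebo. Exits for AEs, if the drug causes any excess, should be more common on deferiprone. When SF exits are much the larger group, the curve and its p-value follow efficacy.

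Two things are at stake. A significant result in the safety section would reflect the ferritin effect. And an excess of AE withdrawals on deferiprone would be diluted in the only planned test that takes the timing of withdrawal into account.

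**Working it through.** **Inputs.** From Protocol 9.2: 64 patients, 1:1 (32 per arm), and 70% v 20% with SF below 1000 µg/L at Month 12, so 30% v 80% reach the threshold. From SAP Section 5: two-sided 0.05. Exit needs a second consecutive value, so it comes one visit after the first. The documents give no AE-withdrawal rate. I assume 5% to 40% over 12 months on deferiprone against 2% on placebo, with exponential timing for both kinds of exit and independence between them.

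**1. The plan's own figure.** The protocol claims power above 90%. By the pooled normal approximation, p̄ = 0.45 and z = [0.5×√32 − 1.96×√(2×0.45×0.55)] / √(0.7×0.3 + 0.2×0.8) = (2.828 − 1.379)/0.608 = 2.38, which gives 99.1%. Exact enumeration of Fisher's test gives 98.3%. The claim holds.

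**2. SF exits expected.** With constant hazards −ln(0.7)/12 and −ln(0.2)/12 per month, an exit by Month 11 requires crossing by Month 10:
- Deferiprone: 32×(1 − 0.7^(10/12)) = 8.2
- Placebo: 32×(1 − 0.2^(10/12)) = 23.6

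**3. Log-rank with SF exits only.** The hazard ratio is ln(0.7)/ln(0.2) = 0.222. With 8.2 + 23.6 = 31.8 events, Schoenfeld's formula gives √(31.8/4)×|ln 0.222| − 1.96 = 2.29, or 98.9%. Simulation of the visit scheme gives 98%. That is close to the 98.3% of the primary Fisher test, with no tolerability difference in the model.

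**4. Adding AE withdrawals at the planned SF rates** (3,000 simulated trials per row; Monte Carlo standard error at most √(0.25/3000) = 0.9 percentage points). Exits are mean numbers, deferiprone/placebo.

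| AE withdrawal, deferiprone v placebo | SF exits | AE exits | SF share of events | As written: favours deferiprone | As written: against deferiprone | AE-only log-rank: against deferiprone |
|---|---|---|---|---|---|---|
| none | 8.3/23.6 | 0/0 | 100% | 98% | 0% | – |
| 5% v 2% | 8.1/23.4 | 1.4/0.4 | 95% | 97% | 0% | 0.2% |
| 10% v 2% | 7.8/23.5 | 2.8/0.4 | 91% | 94% | 0% | 6% |
| 15% v 2% | 7.6/23.5 | 4.2/0.4 | 87% | 88% | 0% | 20% |
| 20% v 2% | 7.4/23.5 | 5.5/0.4 | 84% | 81% | 0% | 40% |
| 30% v 2% | 7.0/23.4 | 8.4/0.4 | 78% | 58% | 0% | 76% |
| 40% v 2% | 6.5/23.3 | 11.1/0.4 | 72% | 33% | 0% | 93% |

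Repeat simulations of the 20% v 2% case put the chance of favouring deferiprone between 78% and 82%. The AE-only column censors at SF exit.

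**5. Other SF rates (assumed).** If 30% v 50% reach the threshold, the test as written favours deferiprone in 16% of trials at AE withdrawal of 10% v 2%, and in 5% at 20% v 2%. It goes against deferiprone in 0.2% and 0.9%, compared with 13% and 55% for the AE-only test. If 50% v 50% reach it, the figures at 20% v 2% are 12% as written and 55% AE-only. A significant result for deferiprone therefore depends on an SF effect near the planned size. The dilution of an AE signal does not.

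**6. Crude percentages are not a full substitute.** With equal AE hazards (10% v 10%) and the planned SF rates, about 2.8 AE withdrawals are observed on deferiprone and 1.9 on placebo, because placebo children leave earlier and are at risk for less time.

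**The case against.** The strongest reply is that tolerability withdrawals are already covered. They are tested in SAP 5.7.2, summarised with a p-value in Table 14.3.1.1, broken down by reason in Table 14.1.4 and listed with timing under 5.7.1. This stands. A reader might infer that an AE excess would go unseen, and the documents do not support that: it would be obscured only in this one curve. What these outputs lack is a comparison that allows for unequal follow-up (step 6).

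A second reply is that the analysis is minor: it is an appendix output, and time to withdrawal is not a named endpoint. This also stands. Nothing in either document says longer retention will be presented as a safety benefit, so a prediction that it will be would rest on a section heading alone.

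A third is that 5.7.7 never says SF exits count. Protocol 3.1 and SAP 3.1 describe reaching the threshold as one of two ways participation ends, which leaves room to code these children as completers. That is fair as far as it goes. But Protocol 4.5, SAP 4.1.1 and SAP 5.2.2 all call the exit a withdrawal, and 5.7.2 shows that the SAP names AEs when it means to restrict. Counting SF exits is the plain reading, and the ambiguity is a further reason to define the event.

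**Conclusion.** The point holds. On its plain wording, 5.7.7 is an all-cause test in which SF exits make up 72% to 100% of events across the scenarios at the planned SF rates. It significantly favours deferiprone in about 98% of trials with no tolerability difference, and in about 78% to 82% with AE withdrawal of 20% v 2%. It mostly repeats the efficacy log-rank in SAP 5.6 and cannot be interpreted for tolerability.

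It would go too far to say that the test carries no information on tolerability. AE withdrawals are events too, and the chance of favouring deferiprone falls from 98% to 33% as assumed AE withdrawal rises from none to 40%. The signal is swamped but present.

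The 98% rests on the protocol's 70% v 20% and on exponential timing. The figures with AE withdrawals also rest on assumed rates and on independence of the two kinds of exit. The primary analysis and the named endpoints are unaffected. The change is worth making before the analysis is run.

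**What to change.** In SAP 5.7.7:
- Define two events: withdrawal due to AE and, separately, withdrawal for any reason other than confirmed SF of 1000 µg/L or more.
- For each, use a cause-specific log-rank that censors at SF-driven exit, and state this censoring rule.
- Show cumulative incidence by arm with SF-driven exit as a competing event. These curves can differ even when the AE hazards are equal (step 6), so they describe and the log-rank compares.
- Label any all-cause curve descriptive, without a p-value.
- State that power for the AE-only test is low (about 6% at 10% v 2% and 40% at 20% v 2%), so a non-significant result is not evidence of equal tolerability.

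A separate row for SF-driven exit in Table 14.1.4 would help the reader but is optional, since the existing reasons and detail column can hold it.

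The cost is a few lines of SAP text, a recoded status variable for each event and the cumulative incidence display. No data collection changes and no named endpoint is lost.
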